4. *Morning neurocognitive function assessments*: Participants will complete motor sequence testing and a verbal word pairs task.
5. *Psychomotor Vigilance Test*: Objective assessment of brain function will be done using 10-minute psychomotor vigilance test (PVT).
6. Karolinska Sleepiness Scale (KSS): A sleep questionnaire.

Participants with obstructive sleep apnea will return to the sleep laboratory for two additional overnights. Subjects will be randomized to receive oxygen or room air during overnight 2 and 3. An Imaging visit will be completed by both sleep apneics and non-sleep apneics. This imaging visit will happen after overnight 1 and before either overnight 2 or overnight 3.

Imaging Visit 1 (MRI and PET Scan) (2hours)

The MRI and PET scan of the brain will occur on a separate day or evening from the sleep studies at the Radiology Imaging Laboratory.

1. *Questionnaires*. Before the scan, participants will complete a MRI Recruitment Safety form. Subjects will also be given the Spielberger State Anxiety Scale, a 20 item assessment used to measure current anxiety; the scale will be used to determine if the subject is safe to enter the MRI scanner.
2. *Structural Clinical Interview* (CSM-IV Axis 1 Disorders (SCID)) — A structural interview to identify a history or current diagnosis, of Axis 1 mental health disorder, which will be given at intake into the study.
3. *MRI and PET Scans*. MRI will be conducted to provide a structural image suitable for coregistering the PET image and observing white matter integrity. The scan should take 35 minutes. These will be MPAGE images collected using the standard ADNI protocol at the in-house 3T MRI scanner at the UCSD Altman Clinical and Translational Research Institute (ACTRI). The PET scan should take 70-90 minutes.

The proposed study evaluates PET results in subjects with cognitive memory impairment and in normal volunteers. Each subject will be asked to come to the MRI/PET center for a single visit lasting approximately two hours. [18F]MK-6240 will be used for amyloid assessment.

[18]MK-6240 is to further characterize the brain pathology by looking at the second potentially deleterious

protein of Alzheimer's, which is Tau protein.

[18F]MK-6240

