MK-6240 has been developed as a second-generation, non-invasive tool for precise spatial and temporal quantification of NFTs in human brain using radioligand PET, designed for improved imaging capabilities compared to other tracers. MK-6240 is a non-biological, small molecule, low molecular weight, high specific activity [18F]-radiolabeled PET tracer ([18F]MK-6240) that is classified by the Food and Drug Administration (FDA) as a Type 1 radiopharmaceutical and by the European Union (EU) as a Class IIb radiopharmaceutical. An intravenous (IV) formulation of [18F]MK-6240 will contain $\leq 20 \mu\text{g}$ MK-6240 in a sterile solution of up to 10% (v/v) ethanol, and 0.5% sodium ascorbate in saline (0.9% sodium chloride) not more than 10 mL total volume. Given the short half-life ($t_{1/2}$) of 18F (~ 110 minutes), [18F]MK-6240 will be locally synthesized, purified, and formulated when required for administration to human subjects, according to pre-specified radiopharmaceutical doses and quality assurance procedures that conform to accepted standards in the field. It is shipped to the California Protons center in Sorrento Valley in a shielded container.

[figure not shown]

Figure 1. Coronal section displaying hippocampal and parahippocampal areas of interest.

The protocol will entail the injection of MK-6240 administered by intravenous bolus injection (over 45-60 seconds) followed by an uptake phase of 45-50 minutes during which time the subject will wait in a quiet room. The PET scan will begin at approximately 50 minutes. Brain images will be acquired continuously for a period of 20 minutes as four 5-minute frames. The images will be immediately assessed for technical validity. If considered inadequate, the subject will have an additional 20 minutes of continuous imaging, collected as four 5-minute frames. A transmission scan will also be collected to allow for reconstruction of the images after the scan. As we have done to date in ADNI, we will use a common iterative reconstruction approach for all scans. The transmission scan is 6 minutes in length.

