Aim 3: We have powered this aim based on the literature, our experience and that of our imaging collaborators. The techniques to acquire structural images of the brain are well established, but the sensitivity of these techniques to changes induced by alleviating hypoxemia/OSA is less clear. Although we have chosen hippocampal volume as our primary measure (outcome)²⁰⁰, we will assess other brain regions for possible use in future studies. We will further quantify beta-amyloid neuritic plaque density and tau protein using PET scanning to assess the impact of OSA on predictors of AD. We will focus on the hippocampus and medial temporal lobe and other regions showing evidence of tau accumulation in the preclinical phase^{313,314}. Given the multiple comparisons inherent in our exploratory aim assessing the entire brain, we are not powered for brain structures beyond our primary outcomes. Based on our prior work, with $n=20$ per group, we have $\text{power}>80\%$ with $\alpha=0.05$ to find a hippocampal volume difference of 0.3 vs. 0.4 (as %ICV – intracranial cavity volume) with $\text{SD}=0.03$ which is a clinically important difference i.e. associated with measurable memory differences²⁰⁰. For amyloid PET imaging, with $n=20$ per group, we will have $>80\%$ power with $\alpha=0.05$ assuming $\text{SUVr}=1.53$ ($\text{SD}=0.18$) to show a clinically important difference of 0.2 between OSA and matched non-OSA³¹⁵. Further, we will use the preliminary data obtained from this aim to design further rigorous brain imaging studies in the future.

The interpretation of this aim will be based primarily on the hippocampal outcomes and the amyloid and tau quantification. [name] (Co-I) is a neuroimaging expert who will oversee these analyses with [name]

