15. POTENTIAL RISKS

Potential Risks to the Subjects, and Procedures to Minimize Risk:

1. Standard PSG: The nasal cannula, respiratory belts, electroencephalography, ECG and oximeter used to monitor sleep and breathing may be mildly uncomfortable and could interfere with normal sleep. Thousands of routine sleep studies are conducted every night across the country without incident.
2. Sleeping with PAP therapy: While generally well tolerated, subjects may experience temporary drying of the nose, mouth, or throat, nosebleed, bloating, ear or sinus discomfort, eye irritation, and skin rashes. Subjects who use PAP therapy nightly may experience sleepiness after the overnight is completed. Participants will be cautioned against drowsy driving and will be encouraged to be driven home by a responsible adult. They will be offered *ad libitum* sleep prior to leaving as needed.
3. Risk Associated with O2: While generally well tolerated, subjects who use Supplemental Oxygen may experience temporary drying of the nose, mouth, or throat, nosebleed, bloating, ear or sinus discomfort, eye irritation, and skin rashes.
4. Risks Associated with Venipuncture: Subjects may experience pain, discomfort, or infection from venipuncture.
5. Risks Associated with EndoPAT (non-invasive heart function test)/blood pressure test: Subjects may experience temporary pain or discomfort from the tightening of the blood pressure cuff.
6. Risks Associated with IV catheter: Subjects may experience infection, phlebitis (vein irritation), and infiltration/extravasation.
7. Psychological Risk: It should be noted that volunteers are often motivated by altruistic feelings and are usually cooperative with studies that serve to develop a better understanding of dementia. Some patients will seek to provide their raw imaging data to their physicians, and, if so, we will release the raw imaging data to the patient, which they can provide to their doctor. This will be true of MRI but not tau PET, as the latter involves an investigational drug. We do not feel that these studies pose any significant psychological risk for the patients.

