Estimated exposure is 5.5 mSv for the F-18 MK-6240. The additional exposure from the low dose PET scan for attenuation correction is 1 mSv. Therefore total patient radiation exposure from the procedure is estimated to be 6.5 mSv. This amount is more than you would receive from one year of natural exposure in the San Diego area, which is approximately 1.6mSv. Cumulative exposure from radiation may increase your risk of developing certain types of cancer in the future.

The total exposure for the study will be 6.5 mSv.

Additional uncommon side effects reported were nausea, dysgeusia (bad taste in the mouth), flushing, pruritus, urticaria, and infusion site rash. Musculoskeletal pain in the neck, shoulder, and back, fatigue, anxiety, claustrophobia, insomnia, dizziness, chills/feeling cold, and hypertension were also reported. The PET imaging procedures could pose unknown risks to a fetus. Therefore, all women of childbearing potential will need to have a negative urine pregnancy test within 7 days of the PET imaging procedures. PET participants may have discomfort, bruising, fainting, or infection from the venipuncture used to administer the tracer compound.

9. Risks of an Incidental Finding: The MRI scan protocol has been designed for research purposes, not for clinical diagnostic purposes. All analysis will be done only by research staff for the purposes of this research study only. The scans will not be reviewed by a radiologist. However, it is possible that an abnormality may be identified. In that case, a written report of the abnormality will be shared with the subject and their doctor.

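### Aim 3 promises and powers an amyloid PET outcome, but the only tracer the protocol describes is a tau tracer

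*Combined protocol and SAP*

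**What the plan says.** **The outcome.** Section 6 (Aim 3) plans to relate medial temporal amyloid and tau to OSA severity and to neurocognitive function. Section 7 (Importance of Brain Imaging) describes the imaging as structural MRI with amyloid and tau PET. Section 10 (Aim 3) names hippocampal volume as the primary measure and adds PET quantification of both proteins. It powers amyloid at 20 per group, assuming SUVr 1.53 with SD 0.18, "to show a clinically important difference of 0.2 between OSA and matched non-OSA". It then bases the interpretation of the aim mainly on the hippocampal results together with the amyloid and tau results, and proposes plaque density as a metric for later longitudinal studies.

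**The tracer.** Section 9 (Imaging Visit 1) states that "18F]MK-6240 will be used for amyloid assessment". The next sentence says the same compound "is to further characterize the brain pathology by looking at the second potentially deleterious" "protein of Alzheimer's, which is Tau protein". The tracer description that follows calls it a "non-invasive tool for precise spatial and temporal quantification of NFTs in human brain using radioligand PET". Section 15, on releasing raw images to patients, says: "This will be true of MRI but not tau PET, as the latter involves an investigational drug".

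**The logistics.** Section 9: "Each subject will be asked to come to the MRI/PET center for a single visit lasting approximately two hours". Section 15 adds 5.5 mSv for MK-6240 and 1 mSv for the attenuation scan, and concludes: "The total exposure for the study will be 6.5 mSv". The IND cited in Section 16 is for MK-6240. Section 21 pays for one imaging visit. Section 11 plans 40 imaging participants, 20 with OSA and 20 without.

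**The concern.** An outcome with its own power statement needs a procedure that produces it, and the protocol describes none for amyloid. The one sentence that assigns a tracer to amyloid is contradicted by the sentence after it, by the tracer description and by the risk section.

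At stake is a promised part of Aim 3. The team could reach analysis with a powered amyloid comparison and no amyloid data, while the molecular measure it does obtain, tau, has no stated SD, target difference or power. The SUVr mean and SD in Section 10 are given for amyloid and say nothing about tau variability. If an amyloid scan is in fact intended, the study's stated radiation total leaves it out.

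**Working it through.** **Step 1. Reproduce the plan's power figure.** Inputs from Section 10, Aim 3: n = 20 per group, difference 0.2, SD 0.18, alpha 0.05. The test and its sidedness are not stated; I assume a two-sided two-sample t test with a common SD.

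- Standardised difference: 0.2 / 0.18 = 1.11.
- Noncentrality: 0.2 / (0.18 × √(2/20)) = 0.2 / 0.0569 = 3.51, on 38 degrees of freedom.
- Power: 92.8% by noncentral t, 94.0% by normal approximation. One-sided, 96.4% and 96.9%.
- Smallest n for 80% power, two-sided: 14 per group (t), 13 (normal).

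The claim of more than 80% reproduces with margin. The arithmetic is not at fault.

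**Step 2. Look for a procedure that yields amyloid.**

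| Item | What the documents give | Covers |
|---|---|---|
| Formulation, injection, acquisition (Section 9) | MK-6240 | Tau, by the protocol's own description |
| Effective dose (Sections 9 and 15) | MK-6240 | One tracer |
| Study radiation total (Section 15) | 5.5 + 1 = 6.5 mSv | MK-6240 plus attenuation scan |
| Supplier and IND (Section 16) | MK-6240 | One tracer |
| Imaging visits (Sections 9 and 21) | One, about two hours | See timing below |

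Timing, from Section 9: the MK-6240 scan starts at about 50 minutes and lasts 20, so it ends at 50 + 20 = 70 minutes, or 90 if the 20-minute repeat is needed. That is the whole 70 to 90 minutes allotted to PET. Adding the 35-minute MRI gives 105 to 125 minutes, which is the stated visit length. The written schedule leaves no room for a second tracer.

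**Step 3. What 20 per group means for tau.** The documents give no tau SD, target difference or summary measure, so only a standardised figure is available. At n = 20 per group, two-sided alpha 0.05 and 80% power, the detectable difference is 0.91 SD. On the amyloid inputs that would be 0.91 × 0.18 = 0.164 SUVr, but nothing supports using 0.18 for tau. If a tau difference of 0.2 is assumed purely for illustration, power depends on the unknown SD:

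| Assumed tau SD | Power |
|---|---|
| 0.18 | 92.8% |
| 0.20 | 86.9% |
| 0.25 | 69.3% |
| 0.30 | 53.8% |
| 0.40 | 33.8% |

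**Step 4. Check the primary measure.** Hippocampal volume, 0.3 against 0.4 with SD 0.03: 0.1 / 0.03 = 3.3 SD. At 20 per group, power is essentially 100%. The PET problem does not touch it.

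**The case against.** The best case for the plan is that this is lost text rather than a missing scan. Section 9 calls tau the second protein without describing a tracer for a first. Section 15 warns of allergy to tracers in the plural, and Section 7 plans PET for both proteins. The document also carries editing residue: stray deletion marks in Section 15 and a sentence spliced into another in Section 16. The imaging logistics are loosely edited too. Sections 9 and 15 give different MK-6240 activity and exposure figures, which need reconciling in their own right.

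This stands as a limit on what can be inferred. A reader might conclude that none of the 40 imaging participants will have an amyloid scan. The documents show only that none is described. For the same reason, deleting amyloid should not be the default remedy.

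A reader might also infer that tau values would be analysed and reported as amyloid. That is unlikely: the sentence after the faulty one names tau, the tracer description says tangles, Section 15 says tau PET, and Section 10 treats the two proteins as separate quantities. A missing amyloid result is the more realistic consequence.

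Finally, Aim 3 is groundwork for a later trial, so the absence of a power statement for a non-primary tau measure is not an error in itself. It matters here because tau may be the only molecular outcome left.

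The lost-text explanation does not remove the problem. Correcting the tracer sentence alone would still leave a powered outcome without a tracer, scan time or disclosed exposure.

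**Conclusion.** The point holds for the protocol as written and should be fixed. The amyloid outcome of Aim 3 and its power statement have no described measurement behind them. The power figure is numerically correct (about 93%), but its inputs cannot be transferred to tau.

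The scope is limited. A reader might take this as a failure of Aim 3 as a whole, and the documents do not support that: hippocampal volume is the primary measure, Hypothesis 3 concerns hippocampal size alone, and tau PET is fully described. Amyloid is still not incidental, because Section 10 makes it part of the main interpretation of the aim.

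The conclusion rests on the text alone, with no other tracer documented elsewhere. The numbers assume a two-sided two-sample t test with equal SDs and complete data on 20 per group.

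**What to change.** Correct the tracer sentence in Section 9 to say that MK-6240 measures tau. Then reconcile Section 6 (Aim 3), Section 7 (Importance of Brain Imaging), Section 9 (Imaging Visit 1), Section 10 (Aim 3) and the exposure text in Section 15 in one of two ways, according to what is actually intended.

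- **(a) No amyloid scan is done.** Remove the amyloid outcome, its power sentence and its interpretation. Name the tau summary measure. State that 20 per group gives 80% power only for a tau difference of about 0.9 SD, and that no tau SD or target difference is available.
- **(b) An amyloid scan is intended.** Describe its tracer, visit, acquisition and radiation exposure, and update the 6.5 mSv study total. The existing amyloid power sentence can then stay. The tau sentence in (a) would still be useful.

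Option (a) costs wording and the open surrender of an amyloid claim, along with part of the aim's rationale, that the protocol as written cannot support. Option (b) costs a fuller imaging section and a revised exposure statement. The documents give no figures from which to size the added scan.

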Vital signs will be taken immediately prior to administration of MK-6240 (within 5 minutes prior to injection) and again at the end of the study visit, prior to discharge (approximately 70 minutes after MK-6240 administration). Subjects will be observed continuously for signs of adverse events or serious adverse events. Subjects who experience an adverse event will not be discharged until the event has been resolved or stabilized. The injection site will be observed for excessive inflammation or damage to the surrounding tissue. A board certified physician ([name]) or physician's qualified designee (Alzheimer's Disease Research Center) will see the patient prior to discharge. The patient will be given the contact information of the ADRC, where phone calls can be directed to [name] for any questions or concerns after the scan.

Rationale for Dosage

[18F]MK-6240

Based on data obtained of a one single IV administration of [18F]MK-6240 no differences in dosimetry, biodistribution, pharmacokinetics or pharmacodynamics are anticipated between the different formulations. The average (\pm SD) value of effective dose (ED) was $29.4 \pm 0.6 \mu\text{Sv/MBq}$, which is in the typical range for 18F-

radiolabelled ligands. Based on this, the administration of 160 MBq (4.3 mCi) of [18F]MK-6240 for PET scanning (including CT scanning) is anticipated to result in a total human ED of about 4.8 mSv.

[18F]MK-6240 was generally well-tolerated. No clinical adverse events (AEs) were observed. No clinically significant abnormalities were noted in physical examinations, laboratory safety tests (chemistry, hematology, urinalysis), vital signs (VS), or electrocardiograms (ECGs). There were no serious adverse events (SAEs), events of clinical interest (ECIs), deaths, or discontinuations due to an AE.

Overnight Visit 2

Participants with obstructive sleep apnea will return to the sleep laboratory for an overnight sleep study and complete the following:

- *Neurocognitive function assessments:* Participants will complete motor sequence testing and a verbal word pairs task.
- *Psychomotor Vigilance Test:* Objective assessment of brain function will be done using 10-minute psychomotor vigilance test (PVT).

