8. MRI testing: There are no known long or short-term risks of MRI. However, precautions must be implemented in order to exclude subjects with absolute contraindications to MRI, which include a cardiac pacemaker, metal fragments in the eyes, skin, body; heart valve replacement, brain clips; being a sheet-metal worker or welder; aneurysm surgery, intracranial bypass, renal aortic clips; prosthetic devices such as middle ear, eye, joint or penile implants; joint replacements; hearing aid, neurostimulator, insulin pump; I.U.D., being pregnant or trying to become pregnant; shunts, stents, metal mesh/coil implants; metal plate, pins, screws or wires, or any other metal implants; permanent eyeliner, eyebrows. Any positive indication by the subject will result in exclusion. FDA guidelines will be strictly followed as to the maximal amount of radiofrequency energy that is deposited in tissues. Some subjects may feel claustrophobic and will be allowed to exit the scanner (with assistance from the investigators) whenever they wish. Subjects will be required to wear hearing protection to minimize the noise exposure from the scanner.

Incidental Findings: There is a risk of incidental findings that can be identified throughout the study.

Examples include, but are not limited to, abnormal EKG observed during the sleep study, abnormal resolution in the MRI, abnormal EndoPAT, etc. If any significant, unknown findings are seen the PI will reach out to the subject to provide consultation. The subject will be given their results in a written report and asked to follow up with their primary care physician.

Fluorine (MK-6240) PET imaging:

Scanning with Fluorine labeled MK-6240 involves injection of 5 mCi of tracer. Participants may have discomfort, bruising, fainting, or infection from the venipuncture used to administer the tracer compound. Other risks of the test include discomfort if the participant is claustrophobic or uncomfortable with needles. It is also possible to have an allergic reaction to the tracers. Total radiation exposure due to imaging studies is as follows:

F-18MK-6240

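### Sections 9 and 15 give incompatible injected activities (160 vs 185 MBq) and total radiation exposures (4.8 vs 6.5 mSv) for the same single MK-6240 PET scan

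*Combined protocol and SAP*

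**What the plan says.** The combined protocol and SAP states the tracer activity and the radiation exposure in two places.

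**Section 9, Research Design and Methods, under the dosage rationale.** A tracer coefficient of 29.4 ± 0.6 µSv/MBq is cited from earlier single-injection data. From it the protocol moves to "the administration of 160 MBq (4.3 mCi) of [18F]MK-6240 for PET scanning (including CT scanning", which "is anticipated to result in a total human ED of about 4.8 mSv".

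**Section 15, Potential Risks, under MK-6240 PET imaging.** Here "Scanning with Fluorine labeled MK-6240 involves injection of 5 mCi of tracer". The exposure is then built up in parts: "Estimated exposure is 5.5 mSv for the F-18 MK-6240"; "The additional exposure from the low dose PET scan for attenuation correction is 1 mSv"; and "The total exposure for the study will be 6.5 mSv". The same 6.5 mSv is given as the total for the procedure and for the whole study.

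Both places concern one scan. Section 9 describes a single imaging visit with one bolus injection, and Section 16 describes a single administration. The description of the injection itself in Section 9 gives no activity and refers only to doses specified in advance. Section 11 plans imaging for 40 participants, 20 with OSA and 20 without.

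**The concern.** Injected activity is something done to each imaged participant, and total effective dose is the number on which the radiation risk is judged. Section 16 calls that risk low without saying which total it has in mind. Someone who takes the planned injection from the dosage rationale would assess 4.3 mCi and 4.8 mSv; someone who reads the risk section would assess 5 mCi and 6.5 mSv. The two cannot both describe the same scan unless the protocol allows a range of activities, a second injection or different handling of different participants, and it provides for none of these.

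The component other than the tracer is also unsettled. Section 9 calls it a transmission scan in the acquisition description and CT in the dosage rationale, while Section 15 calls it a low-dose PET scan. A reader cannot be sure that these are the same thing, or what exposure belongs to it.

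**Working it through.** **Inputs**
- Tracer coefficient: 29.4 ± 0.6 µSv/MBq (Section 9).
- Section 9: 160 MBq, 4.3 mCi, total about 4.8 mSv including CT.
- Section 15: 5 mCi, tracer 5.5 mSv, attenuation correction 1 mSv, total 6.5 mSv.
- Unit conversion: 1 mCi = 37 MBq.

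**Formula**

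Total dose = activity (MBq) × coefficient (µSv/MBq) ÷ 1000 + CT or attenuation component (mSv).

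**Step 1. Section 9 on its own terms**
- 160 ÷ 37 = 4.32 mCi, which agrees with 4.3.
- Tracer: 160 × 29.4 ÷ 1000 = 4.70 mSv. Over ±1 SD of the coefficient: 160 × 28.8 ÷ 1000 = 4.61, and 160 × 30.0 ÷ 1000 = 4.80.
- Left for CT within 4.8 mSv: 4.80 − 4.70 = 0.10 mSv, with a range of 0 to 0.19. The protocol does not state this residual. It comes from subtracting from a rounded total, so only its rough size carries meaning.

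**Step 2. Section 15 on its own terms**
- 5 × 37 = 185 MBq.
- Tracer: 185 × 29.4 ÷ 1000 = 5.44 mSv (5.33 to 5.55 over ±1 SD), which agrees with 5.5.
- Stated sum: 5.5 + 1 = 6.5 mSv. From the coefficient: 5.44 + 1 = 6.44 mSv, which agrees with 6.5.

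Each tracer figure is thus reproduced from its own activity.

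**Step 3. The two sections compared**

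| | Section 9 | Section 15 | Ratio |
|---|---|---|---|
| Activity (MBq) | 160 | 185 | 1.16 |
| Tracer dose from coefficient (mSv) | 4.70 | 5.44 | 1.16 |
| CT or attenuation (mSv) | residual of about 0.1 (0 to 0.19) | 1 (stated) | – |
| Stated total (mSv) | about 4.8 | 6.5 | 1.35 |

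The totals differ by 6.5 − 4.8 = 1.7 mSv. Of this, 5.5 − 4.70 = 0.80 mSv goes with the activity (0.74 mSv if both tracer doses are taken from the coefficient: 25 × 29.4 ÷ 1000). About 1 − 0.10 = 0.90 mSv goes with the other component.

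**Step 4. Does changing one component bring the totals together?**
- 160 MBq with the 1 mSv of Section 15: 4.70 + 1 = 5.70 mSv (5.61 to 5.80 over ±1 SD), not 4.8.
- 185 MBq with the residual of Section 9: 5.44 + 0.10 = 5.54 mSv, not 6.5.

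No. The sections conflict on the activity, and separately on what is added to the tracer dose.

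**The case against.** The best defence is that the two texts have different jobs. The dosage rationale draws on earlier tracer data and is followed by past-tense tolerability results, so 160 MBq might have been carried over from that source. Section 15 says directly what the study scan involves. This reading is possible, but the sentence with 160 MBq looks forward to an anticipated exposure and is the only injected activity in the methods section. Nothing tells the reader to set it aside.

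A second defence is that nobody is shown to be under-informed. This stands. Section 15 is consistent within itself and carries the higher total. A reader might infer from the mismatch that the risk figure is wrong or understates exposure, but the documents do not support that. Both totals also exceed the 1.6 mSv annual background that Section 15 uses for comparison (4.8 ÷ 1.6 = 3.0 years' worth; 6.5 ÷ 1.6 = 4.1), so that comparison survives either way.

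Third, the residual of about 0.1 mSv should not be presented as a stated CT exposure. That is right. The firm point is narrower: 1 mSv does not fit within 4.8 mSv at 160 MBq. If CT and attenuation correction are different components, the plan still has to say so, because Section 9 says its total includes CT and Section 15 presents 6.5 mSv as everything.

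Finally, none of this touches sample size, power, endpoints or analysis. That is true; the point concerns what is administered and what is disclosed.

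**Conclusion.** The point holds as a contradiction between sections. For one MK-6240 scan the protocol gives 160 and 185 MBq (ratio 1.16), and about 4.8 and 6.5 mSv (ratio 1.35, a gap of 1.7 mSv). At least one statement cannot describe the planned procedure, and the documents do not show which. It bears on a planned 40 imaging participants, which is a recruitment target and not a count of people scanned.

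A reader might also infer an arithmetic error. There is none: both tracer figures follow from their own activity and the same coefficient.

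The conclusion assumes one injection per participant, as Sections 9 and 16 describe, and that CT in Section 9 and attenuation correction in Section 15 refer to the same part of the procedure. The second assumption matters only for splitting the gap. The conflicts in activity and in total stand without it. The consent form is not in the reviewed text, so nothing can be said about the total it gives.

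**What to change.** Reconcile the dosage rationale in Section 9 with the MK-6240 text in Section 15, so that the protocol states:

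1. one injected activity, in MBq with the matching mCi, repeated or cross-referenced where the injection is described;
2. one exposure for the CT or transmission (attenuation-correction) component, with its own source and one label throughout, since 29.4 µSv/MBq covers the tracer only and cannot supply it;
3. one total, equal to activity × 29.4 µSv/MBq plus that component, with the sum shown.

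Then check that the participant risk text, including the consent form, carries the same total. Which activity is intended is for the sponsor and investigators to settle; none is proposed here. The cost is wording in the protocol, and in the consent form if it turns out to differ. Design, sample size and analysis are unaffected.
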